1. INTRODUCTION

Alpha-1 Antitrypsin Deficiency (AATD, Alpha-1) is an autosomal co-dominant genetic condition that predisposes to early onset chronic obstructive pulmonary disease (COPD) and liver disease. The *SERPINA1* gene instructs production of alpha-1 antitrypsin (AAT), a protease inhibitor that protects lung tissue from damage due to uninhibited neutrophil elastase. AAT is primarily produced in the liver. The wildtype *SERPINA1* gene encodes for normal AAT type M. Classic severe AATD results from the presence of two deficiency alleles. Numerous deficiency alleles have been reported and the homozygous state for the Z allele (PiZZ) is the most common severe deficiency type. The heterozygous PiMZ state results in a more mild deficiency in serum AAT and thus lower disease risk in most individuals. However, there exists heterogeneity of clinical presentation in most populations of AATD and genetic variation in the Alpha-1 gene has been incompletely studied. Rare gene alterations that predispose to COPD risks of classic AATD in individuals without classic homozygous deficiency genotype have not been studied and are important in understanding, testing and treating at-risk populations.

Demeo et al. showed this heterogeneity between age and smoking status in a study of PiZZ sibling pairs ¹. More recently, Molloy has demonstrated worse lung function in PiMZ individuals who have a history of smoking compared to non-smokers ². In this study of non-index PiMM and PiMZ siblings, there was also found worse lung function associated with PiMZ non-smoking genotypes between MM and MZ subjects. Group mean lung function differences can hide the clinical observation that some PiMZ individuals present at young age with classic panlobular emphysema similar to PiZZ AATD. Mechanisms to detect the genetic signatures that are associated with these advanced clinical phenotypes would allow improved diagnostics and therapeutics for these individuals' lung disease.

Genetic variation in the Alpha-1 gene has been incompletely studied. While historical texts suggest ~100 different SERPINA1 alleles, modern genetic databases remain largely proprietary to each lab but > 500 AAT alleles are now estimated. This biases against publication of new variants. Of some interest is the ability to sequence upstream and downstream from the coding sequence of *SERPINA1* which has allowed detection of significant deletions of major portions of the gene. With this background we hypothesize that *SERPINA1* gene sequencing performed through the DNA1 testing platform will find important sequence variations in individuals who have COPD compared to age, race, sex, AAT level and smoking status matched individuals who do not have COPD in the PiMZ ACT cohort.

The Alpha Coded Testing (ACT) Study is an established and confidential home genetic testing study for alpha-1 antitrypsin deficiency (AATD). Two primary populations choose to test through ACT. This is a preferred program for individuals in the US to test family members of those who have been found severely deficient. In addition, this test is used by individuals with COPD who choose to test in a confidential manner. The ACT Study is sponsored and endorsed by the Alpha-1 Foundation. As a result of the demographics, 27% of the ACT cohort adults who complete testing are found to have one Z allele (N=4153). The serum levels estimated from these blood spot cards are non-normally distributed with significant variation.

ACT participants with heterozygous genotype MZ will be invited to participate in this matched-control study. In the absence of spirometry in ACT, the validated COPD severity score³ has been used to define

the presence and grade the severity of COPD from questionnaires. The primary outcome of this study will capture the number and features of *SERPINA1* variants between the two groups and allow correlation to COPD presence and severity.

Specific Aims

- 1.1 To identify rare *SERPINA1* sequence variants that correlate with presence and severity of COPD in MZ carriers of Alpha-1 antitrypsin deficiency.
- 1.2 To determine the number of individuals who can perform a home test with the DNA1 kit with sufficient blood for analysis.
- 1.3 To correlate COPD severity scores with specific SERPINA1 variants.

This matched-pair pilot study will allow for the number of likely significant gene mutations between COPD and matched control groups to be compared using a paired T-test. Descriptive analysis will link all areas of *SERPINA1* genomic variation with presence and severity of COPD.

2. BACKGROUND

2.1 Literature and Previous Studies

Alpha-1 Antitrypsin Deficiency (AATD, Alpha-1) is the best established genetic risk factor for chronic obstructive pulmonary disease (COPD) and liver disease. COPD represents a major health burden, with nearly 12.6 million individuals in the United States diagnosed. COPD is a significant cause of morbidity, mortality, and related social and financial burden. Understanding heritable and environmental risk factors for COPD is important to guide targeted risk reduction recommendations, detection, and intervention.

AATD-related COPD is phenotypically indistinguishable from idiopathic COPD and approximately 1-3% of COPD is related to severe homozygous AAT deficiency. AATD is an autosomal co-dominantly inherited susceptibility. The *SERPINA1* gene on chromosome 14 encodes production of alpha-1 antitrypsin (AAT), a protease inhibitor that is primarily produced in the liver. The wildtype gene produces the normal AAT protein M, which in circulation is protective to the lungs through inhibition of neutrophil elastase. Two specific *SERPINA1* mutations account for approximately 95% of Alpha-1 deficiency alleles, though over 500 deficiency alleles are now estimated. These common mutations produce the common abnormal AAT proteins S and Z, respectively, which result in corresponding serum deficiency of AAT. Uninhibited neutrophil elastase predisposes to COPD, while the Z protein specifically aggregates in the liver and raises risk for liver disease. Other rare mutations in the *SERPINA1* gene also result in abnormal AAT protein production, leading to serum deficiency or nonfunctional AAT and similar disease risks.

Severe classic AATD occurs in the presence of two abnormal alleles (e.g. ZZ, SZ), where wildtype-deficiency heterozygotes (e.g. MZ, MS) are at lower disease risk; however, there exists heterogeneity of clinical presentation in most populations of AATD and understanding other genetic and environmental modifiers of risk in each group is important. Because AAT production is allele-dependent, heterozygotes, or carriers, have intermediate levels of circulating AAT with values lower than that of homozygous wildtype genotype MM but higher than levels of classic deficiency. The MM genotype corresponds with serum AAT levels of 19.0-59.7 uM, while classic severely affected ZZ individuals have serum levels of less than 11 uM. MZ heterozygote serum levels range from 11 to 48 uM.

Although AAT concentration greater than 11 uM has conventionally been believed to be sufficient, recent data suggest increased susceptibility to COPD among MZ individuals in the presence of additional risk factors. Malloy, et al (2014) found that MZ individuals who smoke are more susceptible to COPD than a control group of matched wildtype MM smokers. In the absence of this other major risk factor studied (smoking), COPD risk was not significantly different between MZ and MM groups. Smoking is the leading environmental modifier of the onset of COPD symptoms in populations with and without AATD.

Some MZ individuals present at a young age with classic panlobular emphysema similar to that which is common ZZ individuals and uncommon in the wildtype population. Group mean lung function differences can hide the clinical observation that some PiMZ individuals appear to be particularly susceptible to an AAT-related phenotype. Genotype is traditionally established by several of paradigms discussed below, yet genetic variation in the Alpha-1 gene has been incompletely studied. Rare gene alterations that predispose to COPD risks of classic AATD in individuals without classic homozygous deficiency genotype have not been studied. Such variants may occur in traditionally untested regions of the SERPINA1 gene and serve as an important genetic modifier of risk in MZ individuals.

Defining both genetic and environmental susceptibility factors is important in understanding, testing and treating at-risk populations. Alpha-1 outcomes are improved in the contexts of presymptomatic risk determination and prompt diagnosis in the presence of clinical symptoms. People who receive presymptomatic genetic testing results consistent with AATD are less likely to adopt cigarette smoking and more likely to quit. Further, occupational choices may be made to minimize exposure to inhaled particulates and early medical care may be sought at the onset of AAT-related COPD symptoms. Among COPD-symptomatic individuals, recognition of underlying AATD is critical, as a primary treatment exists to prevent or delay progression of symptoms in this COPD subpopulation. Augmentation therapy involves infusion of purified human AAT protein and circulating serum AAT levels within normal limits can thus be attained.

Several common AAT testing paradigms exist, including protease inhibitor typing by isoelectric focusing (PI typing), serum quantification of AAT, *SERPINA1* genotyping, and *SERPINA1* next generation sequencing. Pi typing and genotyping can detect the common deficiency protein types and genotypes, respectively. These methods ascertain the majority of carriers and classically affected individuals and correctly assign genotype in most cases. Serum AAT quantification does not definitively determine genotype; however, an unusually low AAT level when only one or no Pi or genotype abnormalities are detected indicates the likely presence of a rare or null allele. Next generation sequencing is a high-throughput and scalable sequencing platform able to clarify genomic sequence of many rare variants within coding regions of the *SERPINA1* gene. A majority of carriers and severely deficient individuals have not had any sequencing test performed. Next generation sequencing in these populations may reveal previously undetected but significant risk variants for Alpha-1.

The Alpha Coded Testing (ACT) study is an established and confidential home genetic testing study for Alpha-1. Over 4,000 MZ individuals have been identified through combined genotyping and AAT quantification. Individuals in ACT provide COPD data and indicate that they are willing to be contacted for possible participation in other research. These individuals have not had *SERPINA1* sequencing so rare genomic variants that may exist in this cohort are previously untested. *SERPINA1* next generation sequencing in MZ individuals with COPD and a control group of matched MZ individuals without COPD will be conducted to determine whether rare *SERPINA1* genetic signatures are biomarkers for presence and severity of MZ-associated COPD.

2.2 Rationale for the Study

Since it is largely unknown why some PiMZ individuals develop COPD similar to that of classic PiZZ Alpha-1 and which is rare in the general Pi MM population, we propose to study *SERPINA1* gene sequences in MZ individuals with and without COPD. Smoking has recently been found to be a significant gene-by-environment modifier of COPD risk. COPD and Alpha-1 are both multifactorial conditions, where multiple environmental and multiple genomic factors likely influence individual risk and disease course. Identifying both genetic and environmental contributors is important for improving Alpha-1 knowledge, recommendations and outcomes. This study will look for previously unknown gene-by-gene correlates as possible risk modifiers for COPD in the PiMZ population. Should such susceptibility biomarkers be determined, future screening recommendations may include gene sequencing as a primary screening or diagnostic test, or for such testing to be incorporated into personalized clinical care and management.

2.3 Primary Hypothesis

The overarching hypothesis of the MZ Carrier Genomics study is that *SERPINA1* gene sequencing performed through the DNA1 testing platform will find important sequence variations in individuals who

have COPD compared to age, race, sex and smoking status matched individuals who do not have COPD in the PiMZ ACT cohort.

3. STUDY OBJECTIVES

3.1 Primary Aim:

The number of individuals with additional *SERPINA1* mutations in the PiMZ COPD cohort will be compared to the number of individuals with additional *SERPINA1* mutations in the PiMZ cohort without COPD.

The primary analysis will determine whether *SERPINA1* genetic signatures detected by sequencing correlate with presence of COPD in PiMZ individuals.

3.2 Secondary Aims:

- 3.2.1 To determine the number of individuals who can perform a home test with the DNA1 kit with sufficient blood for analysis. Among people who desire to test, the portion of people able to successfully obtain a sufficient sample in the home setting using a DNA1 test kit will be determined.
- 3.2.2 To correlate COPD severity scores to specific SERPINA1 variants.
- 3.3 To invite participation in the MUSC Alpha-1 Biorepository Participants will be invited to donate to the MUSC Alpha-1 biorepository by submitting samples in provided PAXgene DNA, PAXgene RNA and EDTA plasma tubes. Copies of spirometry will be requested and COPD questionnaire data linked. These biosamples will be linked to the sequence data for longitudinal transcriptional and proteomic data. Biologic samples are stored for future use with permission for study of Alpha-1, genomics and epigenetic factors. A separate informed consent for biorepository participation will be provided to interested individuals (Pro00039387).

4. RATIONALE FOR THE STUDY

4.1 This study seeks to identify sequence changes that predict COPD in MZ individuals. It is unknown why some PiMZ individuals present at early ages with classic panlobar emphysema similar to that seen in classic PiZZ AATD. Previously untested regions of the *SERPINA1* gene may contain sequence alterations that predict this phenotype.

4.2 Invited participants

Participants tested through the ACT study have already been genotyped, AAT level tested, and reported presence or absence of COPD and demographic information. Classic homozygous AATD has been ruled out. Additionally, these individuals have consented to be contacted for possible participation in Alpha-1 and/or genetic testing-related studies. The MZ cohort with the lower quartile of AAT level is selected as the most reasonable first population for a study of this nature that seeks to identify whether previously untested *SERPINA1* variations correlate with COPD. MZ individuals in the lower quartile of level report the highest MZ incidence of COPD, and this cohort of MZs contains sufficient numbers to obtain matched pairs of COPD-affected and control individuals from this target group. Based on findings of this pilot study, studies of this nature may be expanded to include matched pairs from other MZ-level cohorts and other COPD populations in the future. The 25% of the MZ cohort with lowest levels will have A1-PI values from 11 to approximately 16 uM with the median MZ value equal 19.6 uM.

4.3 Use of the DNA1 kit

CSL Behring partnered with Biocerna LLC in 2013 to offer the DNA1 Advanced Alpha-1 Screening (DNA1) test, the only comprehensive Alpha-1 test available that identifies known and unknown clinically relevant genetic variants related to AATD. CSL Behring and has agreed to supply 150 DNA1 test kits for blood collection and perform testing on all returned participant samples in the Biocerna lab in conjunction with this study. Using the DNA1 test kit involves performing a finger stick in the home setting to obtain

spots of blood that are used for testing. Testing includes: clinical chemistry (a blood spot assay to test AAT levels, as well as a C-reactive protein (CRP) to provide full clinical analysis), targeted genotyping (identifies all known, clinically relevant variants, including S, Z, and F), next generation sequencing (sequencing of the SERPINA1 gene to identify unknown variants), and isoelectric focusing (Results compared to genetic results as a confirmatory step). The next generation sequencing includes coverage of the promoter region, exons and intronic splice sites. The variety of genomic variations detected by sequencing of the SERPINA1 gene will likely be large. Biocerna will define if they believe mutations are likely to be in functional regions of the gene, independent of knowing if the patient has COPD or not.

4.4 Administering COPD severity assessment

The St. George's Respiratory Questionnaire (SGRQ) is a COPD assessment that has been shown to correlate well with established measures of symptom level and disease activity. Presence and severity of COPD can thus be assigned for each participant. The COPD severity score collected previously through ACT study participation will be again administered as part of this study. Thus interval reports will be available as a proxy for disease progression for those who may not have spirometry available. Spirometry reports will also be requested and collected, where possible. The COPD severity score is a validated questionnaire-based instrument that is internally consistent, reliable, and appears to capture a broad range of disease severity. The COPD severity score survey may be administered by telephone or as a written questionnaire. COPD data will allow for correlation of COPD presence and severity with genomic findings.

Questionnaires will be formulated in REDCap, with hard copies available for mailing to participants who lack internet access or literacy. Following signed informed consent and HIPAA forms, participants will either be mailed questionnaires to complete and return or will be emailed a secure link for access to REDCap questionnaires, including the SGRQ, COPD severity score and demographic surveys. Any paper survey documents will be digitized, reviewed by a team member to confirm that all pages are present and legible, facing the appropriate direction and are an exact copy of the paper forms. Each page will be individually labeled with the participant's study ID and the question item responses provided will be entered by a trained study coordinator under the participant's ID in the electronic database. The original paper documents will be kept in a locked file cabinet in the Alpha-1 office.

4.5 Invitation to the biorepository

Participants will be asked to check Yes or No on this study's consent form regarding their interest in donating blood to the MUSC Alpha-1 Biorepository. Interested participants will be presented with the separate Biorepository informed consent (Pro39387). Upon providing consent participants who are not on-site at MUSC will be mailed PAXgene DNA, PAXgene RNA, and EDTA plasma tubes that require collection at a physician's office. Overnight return mailing and processing charges are included in study funding. The purpose of the Biorepository is to foster future biological research related to Alpha-1 and genomics. Interest in Biorepository participation does not impact participation in this study.

5. STUDY DESIGN AND PROCEDURES

5.1 Overview

The MZ Alpha-1 Carrier Genomics study is a pilot study that will enroll up to 150 MZ individuals, with a goal of attaining 50 matched pairs. COPD+ and COPD- individuals will be matched on age, sex, race and smoking history. Any consented individuals who do not have a match in the study cohort will be allowed to continue with participation. Their samples will be analyzed as unmatched COPD + or – samples, which will be accounted for statistically and discussed in study reports.

Presence and severity of COPD is assessed by a COPD severity score for each registrant in the ACT database. We will additionally ask as part of this study that current COPD questionnaires and demographic surveys be completed, and that patients submit previous lung function testing if this has been done. Participants will be mailed a DNA1 test kit to obtain and return a blood sample by finger stick for the purpose of *SERPINA1* gene sequencing. Gene sequencing at Biocerna LLC will identify, if present, genomic signatures that may correlate with COPD in this cohort. Biocerna LLC will determine likely pathogenicity of sequence variants detected blinded to knowing COPD-status of the patient tested. Statistical analysis will correlate genetic findings with COPD presence and severity. Participants will receive their results by mail. Participants will also be invited to contribute additional samples to the MUSC Alpha-1 Biorepository.

5.2 Participant Recruitment and Selection

There are over 370 individuals in the ACT MZ cohort with AAT levels below the 25th percentile who have previously provided COPD severity scores. We propose to invite these 370+ individuals to participate. Potential participants will be invited by research staff initially by telephone call, though subsequent contact may occur via alternative methods, including but not limited to email or home mailing per ACT protocol policy procedures. Eligible individuals who did not test through ACT and are able to provide documentation of their MZ and lower quartile level results will also be accepted into this study. The study personnel contacting the participant will describe the nature of the study and details of participation, including that questionnaire based responses, spirometry if available, and a blood sample by finger stick for genetic testing will be requested. Once participants are enrolled (signed informed consent and HIPAA), an email will be sent containing a secure link for recipients to follow to complete the questionnaires on REDCap. If needed, paper questionnaires may be mailed. Test kits will be mailed following receipt of completed questionnaires.

All participants may make a written decision separate from primary study consent and participation whether to allow their clinical and genomic data linked to personal identifiers to be stored in the MUSC Alpha-1 Biorepository indefinitely after the conclusion of this study. No personally identifying information will be published and personal information obtained and stored will remain confidential to the extent possible within State and Federal law.

5.3 Inclusion/Exclusion

5.3.1 Inclusion Criteria

- 1. Signed informed consent
- 2. PiMZ individuals who fall into the lower quartile of AAT levels.

5.3.2 Exclusion Criteria

- 1. Age <18 years
- 2. Known homozygous or compound heterozygous classic severe AATD (e.g. PiSZ, ZZ, Znull)

5.3.3. Conditional Exclusions

1. Incomplete return of study materials. Those who consent but fail to both complete questionnaires and return a blood sample may be excluded from analysis.

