5.6. Study Schedule

1. Following IRB approval and establishment of CSL contracts study coordinators will contact lower quartile MZ individuals by telephone to invite them to participate and schedule informed consent. Follow-up calls may be made to boost initial recruitment and matching.

- 2. For each informed consent and questionnaire set received, a barcoded DNA1 test kit will be mailed with instructions for obtaining and returning the required sample. Postage paid return mailing supplies will be provided.
- 3. The samples returned will go by US Postal Service directly to the Biocerna lab for testing. Biocerna will have the sample and barcode only (no personal health information), while all survey items and identifiers are collected and stored for linkage at MUSC.
- 4. MUSC will perform matching of age, sex, and smoking-status COPD-affected and control MZ participants.
- 5. Biocerna LLC will perform *SERPINA1* sequencing on samples sent by participants and provide laboratory interpretation of likely pathogenicity to study personnel.
- 6. Study personnel will link the results to the participant and mail results to the participant. The results will include a study interpretation of results and recommendations for accessing appropriate resources.

7.

- 8. Statistical analysis of all matched pairs using paired T-test and descriptive analysis will allow for conclusions of this pilot study to be made. Participants for whom no match is available in the study cohort will be included in an uneven COPD+ / arm analysis and aggregate study reporting.
- 9. The study will be complete in approximately 2 years, with subsequent publication of results, including an abstract for the American Thoracic Society annual meeting in May 2016.

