6. STATISTICAL ANALYSIS

6.1 Primary Aim: The number of likely significant gene mutations between COPD and matched control groups will be compared using a paired T-test

The variety of mutations in non-coding and coding regions of the *SERPINA1* gene will be large. Therefore, Biocerna will define if they believe mutations are likely to be in functional regions of the gene, independent of knowing if the patient has COPD or is a matched control. The number of likely significant gene mutations between COPD and matched control groups will be compared using a paired T-test.

6.1.1 The nature of mutations identified will be correlated with COPD severity.

Descriptive analysis at the genomic level will follow to link all areas of genomic variation with severity of COPD. Functional gene expression and likely pathogenicity as determined in Biocerna interpretation will be related to established COPD phenotypes using linear models.

6.2.2 The portion of individuals who return a DNA1 test kit with sufficient blood sample for testing will be quantified for assessment of home testing feasibility.

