6.2 Sample Size

There is not a power analysis associated with this pilot study.

The goal is to analyze 50 matched pairs, or 100 total samples. This study will enroll up to 150 individuals in order to have at least 100 samples returned to the lab for testing, as there are some people who consent but never return their test kit. Enrolling up to 150 allows better chances of finding 50 matched pairs. All samples that are received by the lab will be analyzed. If we end up with uneven numbers in the COPD+ and COPD- arms, more than 100 samples analyzed, or have participants without a match, we will account for this in the statistical analysis and reporting.

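### Could the exclusion rule in Protocol 5.3.3 turn the home-test feasibility figure into one for returners only?

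*Protocol*

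**What the plan says.** The feasibility aim appears in three forms.

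- Protocol section 1, aim 1.2, asks for a count: "To determine the number of individuals who can perform a home test with the DNA1 kit with sufficient blood for analysis".
- Protocol 3.2.1 turns this into a proportion and names its base: "Among people who desire to test, the portion of people able to successfully obtain a sufficient sample in the home setting".
- The item numbered 6.2.2 in Protocol section 6, repeated as item 3 of the SAP, describes the calculation: "The portion of individuals who return a DNA1 test kit with sufficient blood sample for testing will be quantified". It states no denominator.

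The exclusion rule is in Protocol 5.3.3, under a heading about incomplete return of materials: "Those who consent but fail to both complete questionnaires and return a blood sample may be excluded from analysis". It is permissive and does not say which analysis it covers.

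The order of steps is fixed in two places. Protocol 5.2 states: "Test kits will be mailed following receipt of completed questionnaires". Protocol 5.6, item 2, agrees: "For each informed consent and questionnaire set received, a barcoded DNA1 test kit will be mailed".

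Protocol 4.3 says that the kit supplier "agreed to supply 150 DNA1 test kits for blood collection and perform testing on all returned participant samples". Protocol 6.2 (Sample Size) sets enrolment at up to 150, "in order to have at least 100 samples returned to the lab for testing, as there are some people who consent but never return" their kit. It adds that the margin also helps to find 50 matched pairs. Neither document gives an expected return rate or an expected share of returned samples with enough blood.

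**The concern.** For most of this study, a participant without a sample has nothing to contribute: with no sequence there is no genotype to compare. For the feasibility aim the reverse holds, because not sending a sample back is one of the ways home testing fails.

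Three features together make a wrong base look possible. The exclusion rule is not limited to the comparison of genotype with COPD. The calculation sentence can be parsed in two ways, with return as part of the outcome or as the definition of who is counted. And the sponsor expects some non-return, so the affected group will probably not be empty.

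If non-returners were dropped, the reported figure would describe the adequacy of the cards that reached the laboratory. The aim asks how many willing people get through the whole process at home. The narrower figure is always at least as favourable, and a reader who saw only a percentage could not tell which one had been reported.

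**Working it through.** **Plan's own figures.** 50 pairs × 2 = 100 samples, which agrees with Protocol 6.2. The 150 cannot be reproduced independently, because no non-return rate is stated. Solving backwards gives 1 − 100/150 = 33.3% non-return, but that merely restates the two numbers.

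**Effect of the base.** Let r = returned/mailed and s = sufficient/returned.

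- Returners as base: s
- Everyone mailed a kit as base: s × r
- Ratio of the two: 1/r = mailed/returned, whatever s is
- Gap: s × (1 − r)

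With one kit per person, at most 150 people are mailed one. If at least 100 samples come back, the ratio is at most 150/100 = 1.50. With 150 mailed, and r and s **assumed**:

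| Returned | r | Ratio | Gap at s = 80% | Gap at s = 100% |
|---|---|---|---|---|
| 100 | 66.7% | 1.50 | 26.7 points | 33.3 points |
| 120 | 80% | 1.25 | 16.0 points | 20.0 points |
| 135 | 90% | 1.11 | 8.0 points | 10.0 points |

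The algebra is exact, but the sizes are illustrative. The 1.50 divides a planning maximum by a planning minimum, and the maximum was also set with matching in mind. It would be exceeded if fewer than 100 samples came back from 150 kits.

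**Does the plan lead to the returner base?**

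1. *The aim.* Protocol 3.2.1 puts people who want to test in the denominator and those who succeed in obtaining an adequate sample in the numerator. Returners are a subset of the first group, so a returner base does not answer this aim.

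2. *The calculation sentence.* Read with 3.2.1, the sentence in 6.2.2 and SAP item 3 describes success as a kit returned with enough blood in it. Its declared purpose is to assess whether home testing is feasible, which fits that reading. The returner reading is grammatically possible but conflicts with the aim.

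3. *The exclusion rule.* Its wording on failing to do both things has two meanings. Because questionnaires come before the kit, each meaning collapses to one condition:
   - If it means that neither was done, it reduces to no questionnaires, since someone without questionnaires is never sent a kit. Nobody who was mailed a kit can then be excluded, and the mailed-kit figure is unaffected.
   - If it means that not both were done, it reduces to no sample. Mailed non-returners could then be excluded.

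   Each reading makes one of the two clauses redundant, so the order of steps favours neither. The heading gives some support to the second. Even then the rule only permits exclusion, and its evident use is for people who lack the paired questionnaire and sequence data that the COPD analyses need. Removing non-returners from a count of who returned would defeat the purpose of the count.

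4. *Recoverability.* Protocol 5.4 defines enrolment at signed consent. Protocol 5.6 has a barcoded kit sent for each consent and questionnaire set, with samples going to the laboratory under that barcode. The numbers consented, mailed and returned should therefore be available at reporting, and the number sufficient should follow from the laboratory's results.

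**The case for a change.** The strongest case for acting is that 3.2.1 gives only a concept. Wanting to test is not mapped to consented, mailed or returned, and the two places that specify the calculation do not repeat it. Nothing exempts the feasibility aim from 5.3.3. A returner-only figure would thus be a departure from the aim that the text does not expressly forbid. Two or three sentences would close the gap at no cost in data.

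Part of this stands. The operational denominator is unwritten, the wording of 5.3.3 is loose, and stating the denominator with the counts consented, mailed, returned and sufficient would be good reporting practice.

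It does not show that the plan, followed as written, gives a wrong answer. The error needs three choices in sequence: the less natural parse of the calculation sentence, one of two readings of the exclusion rule, and a discretionary use of that rule against a stated aim. Nor is there a single correct replacement. Counting every mailed non-return as a failure mixes inability to collect blood with a change of mind or lost mail, while 3.2.1 speaks of both wish and ability. The choice between consented and mailed as the base is partly a matter of preference.

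**Conclusion.** No change to the plan is needed. The missing detail is one that analysts would fill sensibly. The aim names a base wider than returners, the calculation sentence fits it, and the exclusion rule neither requires nor sensibly allows non-returners to be removed from this count.

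If the narrower base were used all the same, the figure would be inflated by mailed/returned. That factor is at most 1.50 if no more than 150 people are mailed one kit each and at least 100 samples come back, and 1.25 or 1.11 at assumed return rates of 80% or 90%. None of these is an expected value, because the documents give no return or sufficiency rate.

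The stakes are low. The result is descriptive, belongs to a secondary aim of a pilot study, and carries no test or decision threshold. The primary comparison of COPD and control participants does not depend on it. The conclusion rests on reading the calculation sentence together with 3.2.1, and on the counts at each step being kept, as the consent and kit procedures imply.
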